On day 1, the study procedures will be similar to those for inpatient participants. However, the outpatient participants will not receive alcohol prior to the fMRI and will be given take-home mifepristone doses and instructed on at-home medication observation and saliva collection procedures at the end of the day.

On days 2 and 3, participants will be asked to complete a video teleconference with nursing staff or a research coordinator. Video teleconference will be on a HIPAA compliant telemedicine app or website (participant preference) and does not require the participant to enter any potentially identifying information. The participant is free to enter their study ID or a pseudonym to enter the virtual waiting room to connect with the provider. This service uses end-to-end encryption and no identifying information is recorded. On this video teleconference, nursing staff will administer the Systematic Assessment for Treatment of Emergent Events (SAFTEE) (Johnson et al., 2005). This standardized, structured instrument is specifically adapted for use in substance use disorder clinical trials, to collect information on incidence and severity of medication side effects and adverse events. Nursing staff will also administer the adrenal insufficiency questionnaire. Participants will then be observed taking their dose of MIFE.

To determine if the degree of elevation of CORT in response to GR blockade by MIFE correlates with any of our outcome measures, each morning upon wakening and at bedtime participants will be asked to collect a salivary cortisol sample. Baseline samples will be collected on day 1, prior to beginning study medications. Measurement of CORT in saliva is not invasive and multiple samples per day are easily obtained. Unlike serum CORT, salivary CORT is unbound to protein and reflects the physiologically relevant fraction. For each sample, subjects chew a pad for 90 sec, which is then placed into a capped salivette. Saliva is harvested by centrifugation and stored in a cryotube at -70 until assayed in duplicate (Diagnostic Systems Laboratories; Webster, Texas). The intra- and inter-assay coefficients of variation are below 5%. As we expect variability in CORT within and across MIFE doses, these data will be included in our analyses.

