MIFE has a rapid onset of action and achieves peak plasma levels within 1 - 2 hrs of oral dosing. Peak plasma levels and bioavailability increase as a function of dose but are not directly proportional to dose. However, plasma concentrations of MIFE metabolites do increase in direct proportion to dose; metabolites have antiglucocorticoid activity and contribute to long-acting drug effects (Pomara et al., 2002). MIFE is effective with once-a-day dosing. The half-life is 40 hrs following a single dose and 84.6 hrs following multiple doses. Following discontinuation of MIFE, plasma levels are detectable for up to 2 weeks (Heikinheimo et al., 2003). For this study, we selected to use the high MIFE dose of 1200mg, based on recent clinical trials for other neuropsychiatric disorders associated with HPA-axis dysfunction, and that 1200 mg MIFE has been safely administered over extended periods (MIFE Investigator Brochure, Corcept Therapeutics). This study only exposes subjects to MIFE for up to 6 days. We are not planning to reduce MIFE dose during such a brief treatment period. If a subject experiences significant medication side-effects or any serious adverse event or if the participant declines to continue medication, then we will discontinue that participant from the study. It

should be noted that inpatient subjects are under continuous nursing observation throughout the CRU stay and thus adverse events can be identified and addressed rapidly. HC subjects will be instructed to call the study doctor if they have any adverse events. Subjects will be randomized to active MIFE and placebo on a 2:1 ratio.

In the proposed study, MIFE will be administered under an IND ([name] 124365). MIFE (300 mg) and matching placebo will be provided by Corcept Therapeutics, Menlo Park, CA. We will overencapsulate the medication and placebo as necessary. The Johns Hopkins Bayview Investigational Drug Services (IDS) will maintain the inventory and dispense the medication. MIFE absorption and elimination are not affected by age, body weight, BMI, race or sex (Mifepristone Investigator Brochure, Corcept Therapeutics).

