Mifepristone (MIFE) Administration: Since MIFE blocks the progesterone receptor, treatment of a pregnant woman would result in the termination of pregnancy. All females must have a negative urine pregnancy test prior to MIFE initiation; women on hormonal birth control, who are pregnant, nursing or planning pregnancy, and women with unexplained vaginal bleeding are excluded from study participation. In addition, women must agree to use a non-hormonal form of birth control for at least 1 month after stopping MIFE treatment. We will provide female participants with condoms at each outpatient follow-up visit. Women may experience endometrial thickening or unexpected vaginal bleeding; there is a low likelihood of these events.

Due to the anti-progestin effects of mifepristone and given the lack of adequate data on the potential levels of mifepristone in semen, male subjects will be required to employ barrier protection with their female partners. Males should use barrier protection during intercourse for at least 5 half-lives of the drug (half life = 18 hours) plus 90-days (the duration of one spermatogenic cycle in men and residence time for unejaculated sperm) after last dose of mifepristone to avoid risk of anti-progestin effects transmitted to female sexual partners. We will provide male participants with condoms for at least 94-days after the last dose of mifepristone.

Based on prescribing information for MIFE treatment of Cushing Disease, MIFE may produce prolongation of the QT interval of the electrocardiogram (ECG) and use of MIFE with QT interval-prolonging drugs is contraindicated. A recent evaluation of the cardiac safety of three doses of 1200 mg MIFE given every 12 hrs to subjects found no clinically meaningful QT prolongation in healthy subjects (Corcept Therapeutics Investigator Brochure).

Based on data in individuals with Cushing Disease, MIFE may cause adrenal insufficiency. Symptoms of adrenal insufficiency may include abdominal pain, vomiting, muscle weakness and fatigue, depression, extremely low blood pressure (hypotension), weight loss, changes in mood, and shock (adrenal crisis). There has been no evidence of the development of adrenal insufficiency during short-term administration of MIFE doses up to 1200 mg in clinical trials for other psychiatric disorders.

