- Subjects with potassium levels below the normal range at screening will be excluded. We will also monitor potassium on days 1 and 7 (AUD participants only), and at the 1 week follow-up. Potassium will be administered if clinically needed.
- Based on data from studies and clinical trials, which encompass over 1500 subjects and patients treated for one to two weeks with MIFE doses ranging from 300 mg/day to 1800 mg/day, the risk for development of adrenal insufficiency in persons without Cushing Syndrome is low. Specifically, in studies of psychotic depression and in volunteers with antipsychotic drug induced weight gain as well as healthy volunteers and subjects with hepatic and renal impairment who participated in PK, PD, and DDI studies, there were no AEs of adrenal insufficiency reported (Personal Communication, Corcept Therapeutics). Still, in the current study, subjects will be monitored for the development of the signs and symptoms of adrenal insufficiency (weakness, nausea, increased fatigue, hypotension) during the CRU stay and during outpatient visits. Once on the CRU and following MIFE administration, we monitor for hypoadrenalinism by measuring blood pressure and heart rate along with all vital signs q6 hours. For inpatient participants, we also will be asking questions q6 hours regarding emergence of symptoms of hypoadrenalinism, including the development of fatigue, nausea, vomiting, abdominal pain, loss of appetite, light headedness, arthralgias, and myalgias. Outpatient participants will be asked these questions once daily either in person or by phone. If an AUD subject on the CRU is thought to be developing hypoadrenalinism, we will discontinue the MIFE, support blood pressure with intravenous fluids and infuse 8mg of dexamethasone intravenously. Outpatient healthy control participants will be provided with oral dexamethasone 8 mg to take home. They will be given an instruction sheet (see supplemental study documents) that advises them of the symptoms of adrenal insufficiency and advises them to call [name] if these symptoms start to develop. This dose is more than adequate to reverse the glucocorticoid receptor blockade. The proposed single dose of dexamethasone is routinely used in the determining the etiology of Cushing Syndrome. In patients with impaired glucose tolerance or frank diabetes mellitus, this dose of dexamethasone can transiently increase blood sugar; however, in our study, participants with impaired glucose tolerance are excluded. Dexamethasone will only be used in the unlikely event of adrenal crisis in which we do not anticipate any negative side-effects from the treatment.

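### Section 8b gives two conflicting triggers for rescue dexamethasone: suspected hypoadrenalism in an AUD inpatient, and adrenal crisis only

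*Combined protocol and SAP*

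**What the plan says.** The relevant text is one bullet in section 8b of the combined protocol and SAP, under Mifepristone administration. It describes monitoring for adrenal insufficiency. On the unit, vital signs are taken and symptom questions asked every 6 hours; outpatients are asked the questions once a day.

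For AUD inpatients the bullet gives an explicit order: "If an AUD subject on the CRU is thought to be developing hypoadrenalinism, we will discontinue the MIFE", followed by "support blood pressure with intravenous fluids and infuse 8mg of dexamethasone intravenously".

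For the healthy controls it states: "Outpatient healthy control participants will be provided with oral dexamethasone 8 mg to take home". They also receive an instruction sheet that "advises them of the symptoms of adrenal insufficiency and advises them to call" a named clinician if symptoms begin. The sheet is listed as a supplemental study document.

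The bullet then turns to the safety of dexamethasone itself, covering its routine diagnostic use and a possible transient rise in blood sugar. It ends with the sentence at issue: "Dexamethasone will only be used in the unlikely event of adrenal crisis in which we do not anticipate any negative side-effects from the treatment".

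**The concern.** One rescue drug has two stated conditions of use within a single bullet. The first is a clinical suspicion that hypoadrenalism is developing. The second, introduced by 'only', is adrenal crisis. If the second is the stricter condition, a clinician who follows it to the letter would hold back a dose that the first instructs them to give.

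What is at stake is the timing of treatment for a known risk of the study drug. The sponsor took that risk seriously enough to schedule checks every 6 hours on the unit and to send dexamethasone home with outpatients. A rescue instruction of this kind should carry one threshold.

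**Working it through.** No arithmetic applies, and the plan gives no figure to reproduce. The check is a comparison of texts.

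**1. The operative order.** The trigger in "If an AUD subject on the CRU is thought to be developing hypoadrenalinism, we will discontinue the MIFE" is a judgement that a condition is emerging. The monitoring that feeds it asks about non-specific complaints such as fatigue, nausea, dizziness and joint or muscle pain, together with blood pressure and heart rate. That scheme is built to detect the problem early.

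**2. The closing sentence.** Its trigger is adrenal crisis, and 'only' makes it exclusive.

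**3. Are the two triggers the same?** The protocol does not define adrenal crisis. Apart from the closing sentence, the term appears once, in the list of insufficiency symptoms in section 8a (Mifepristone (MIFE) Administration): "extremely low blood pressure (hypotension), weight loss, changes in mood, and shock (adrenal crisis". There it labels shock, the most extreme item in the list. On the protocol's own usage, crisis is a severe form of insufficiency and not another name for suspected insufficiency. The two conditions therefore differ.

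**4. Does any other text reconcile them?** The related provisions are:
- Section 4a, Outpatient procedures for HC: "Nursing staff will also administer the adrenal insufficiency questionnaire".
- Section 4a, MIFE Administration: "HC subjects will be instructed to call the study doctor if they have any adverse events".
- Section 8b: a study physician can be reached by phone, and a neuroendocrinologist will manage care where needed.

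These cover detection, contact and clinical management. None says when dexamethasone is to be given.

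**5. Does the conflict reach the analysis?** No. The closing sentence restricts dexamethasone, not the stopping of mifepristone. Mifepristone is stopped on suspicion under either reading, and section 4a (MIFE Administration) ends study participation when medication is discontinued. The wording therefore bears on patient care and not on the trial's estimates.

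**The case against.** The strongest defence is that the closing sentence was never meant as an instruction. It ends a run of remarks about dexamethasone's own risks and finishes on side effects. Its job is to reassure the reader that exposure will be rare. The order to infuse is explicit, and unit staff would most likely follow it. This stands, and it is why the expected effect on the unit is small.

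It can also be said that the gap between the triggers is narrower than it looks. Adrenal crisis is undefined, and its meaning is inferred from one parenthesis. The inpatient order includes blood pressure support, so it seems to contemplate more than isolated fatigue. This stands in part. It would be an overstatement to describe the contrast as trivial symptoms against shock, but suspicion of a developing condition and a crisis still differ, and 'only' admits just one of them.

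The frequency is also likely to be low. Section 8b reports no adrenal insufficiency adverse events in the studies it lists, within a base of over 1500 people treated for one to two weeks. Section 8a likewise reports no evidence of insufficiency with short-term dosing in trials for other psychiatric disorders. Reported events are not the same as clinical suspicion, so this gives no rate for the trigger, but it does point to rarity.

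A reader might go further and infer that healthy controls at home are told to hold their tablets until they are in shock, because the infusion order is limited to AUD subjects on the unit and the crisis sentence has no such limit. The documents do not support that inference. When a control subject takes the dose may well be set out in the instruction sheet, which was not supplied, and its absence here is not a gap in the plan. The visible text gives these subjects daily questioning, a prompt to call when symptoms start and access to a physician. It also places the take-home supply directly after the inpatient order, at the same 8 mg, which reads naturally as the oral counterpart for the same problem.

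**Conclusion.** The inconsistency is real but minor. One bullet in section 8b orders dexamethasone on suspicion of hypoadrenalism and then restricts it to adrenal crisis, and no other text settles which applies. The suspicion-based order is very probably what is meant.

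This conclusion rests on two readings: that crisis means something close to shock, as its one other use indicates, and that unit staff would act on the explicit order. If the second holds, the practical effect for AUD inpatients is small. For the healthy controls no conflict can be shown; whether their sheet states a matching trigger is an open question.

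How often the wording might alter care cannot be estimated, because the documents give no rate of suspected insufficiency. Any headcount would rest on invented rates. The point is a safety wording correction, with no bearing on design, power or analysis.

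**What to change.** Leave the inpatient order unchanged: stop mifepristone, give intravenous fluids, infuse 8 mg of dexamethasone. Replace the closing sentence of the bullet with:

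*Dexamethasone will be used only if adrenal insufficiency is suspected or in adrenal crisis; we do not anticipate negative side-effects from this single dose.*

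Then check that the healthy controls' instruction sheet uses the same trigger. No new rule on who authorises a dose at home is needed to cure this defect.

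The cost is one reworded sentence and one document check. Visits, dosing, sample size and analysis stay as they are.

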Each subject will participate in an initial assessment, and a possible second assessment visit for completion of medical history, vital signs and laboratory tests. AUD participants will be admitted to the CRU for 6 nights. HC participants, who participate in the study on an outpatient basis, will continue MIFE dosing and salivary sample collection at home. For AUD participants, there are two follow-up visits at 1 and 2 weeks following CRU discharge. For HC participants, there is one follow-up visit at 1 week following the second fMRI. It is anticipated that subjects will complete all study procedures within a 6 month period.

c. Blinding, including justification for blinding or not blinding the trial, if applicable.

Staff and subjects will be blind to the alcohol and MIFE doses administered during this study to reduce expectancy effects.

d. Justification of why participants will not receive routine care or will have current therapy stopped.

Subjects are not seeking treatment for their AUD; they will not currently be engaged in therapy.

e. Justification for inclusion of a placebo or non-treatment group.

A placebo MIFE dose is included for comparison with the active drug effects and to control for expectancy effects.

f. Definition of treatment failure or participant removal criteria.

A participant will be removed from the study if s/he experiences a moderate or severe adverse event, is noncompliant with study or CRU rules, or if it is determined by the study physician to be unsafe to continue.

g. Description of what happens to participants receiving therapy when study ends or if a participant's participation in the study ends prematurely.

MIFE dosing is discontinued at the time of discharge from the study.

5. Inclusion/Exclusion Criteria

Healthy, non-treatment seeking, 21-60 years old, male and female subjects will be recruited through the media. Recruitment uses a mix of newspaper, radio, and on-line advertisements. Based on the 2011 census, the Baltimore metropolitan area is mostly Caucasian (61%) or African-American (30%); the remaining 9% is Asian (4%) and persons reporting two or more races (5%); 8.8% of the population report Hispanic ethnicity.

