COVID infection risk: Study activities will be conducted remotely as opposed to in person when possible to reduce unnecessary in-person encounters. For all in-person visits, we will follow HEIC clinical standards for maintaining staff and participant safety. Staff will use appropriate PPE (face mask/shield, gowns, gloves) and practice physical distancing. Participants will wear face masks. Any equipment that participants are asked to handle to complete study procedures (e.g., MRI compatible response buttons) will be cleaned prior to use. Office spaces will be cleaned by sanitizing surfaces between office visits. We will limit the number of people within spaces (e.g. KKI MRI suite). For procedures that require contact (e.g. phlebotomy, obtaining vital signs), we will limit the amount of time the contact lasts and ensure both staff and patients use appropriate PPE.

A staff member must accompany the participant on the car ride from the JHH campus to the Bayview CRU. Staff and participants will use face masks and physically distance to the extent possible during the ride.

Blood alcohol levels measured by breathalyzer are obtained serially during the alcohol sensitivity session. The staff member running these sessions will be wearing full PPE attire. The staff member will leave the research room each time the participants exhales into the breathalyzer. Participant then removes the disposable mouth piece and places it in a basket containing a red bag designed to hold toxic materials. A fresh mouth piece is attached by staff after re-entering procedure room.

When utilizing both the CRU and the imaging suites, we will follow policies to limit COVID infection exposure risk established by those locations.

c. Plan for reporting unanticipated problems or study deviations.

[name] has responsibility for communication with the JHU SOM IRB and will be responsible for reporting of AEs and SAEs. SAEs that are deemed to be severe and have a high probable or definite relationship to study procedures will be promptly reported to the Johns Hopkins Medical Institute IRB, Corcept Therapeutics, and the FDA.

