[name] also is responsible for notifying Corcept of (a) any serious and/or unexpected adverse drug experiences (as those terms are defined in 21 C.F.R. § 312.32(a), as amended), and (b) all adverse events of special interest (AESI) that occur during the course of the Study no later than twenty-four (24) hours after receipt of such information. AESI shall mean any of the following events, irrespective of the level of severity:

1. Major adverse cardiovascular events including death related to coronary or cerebrovascular disease, acute myocardial infarction, stroke, and revascularization (coronary or cerebral)
2. Retinopathy
3. Endometrial hyperplasia and/or abnormal vaginal bleeding of any cause

The PI shall notify Corcept of all serious adverse events each time that a report is made to the IRB.

d. Legal risks such as the risks that would be associated with breach of confidentiality.

Our staff is well trained in the matters of confidentiality including maintenance of genotyping information. At present there is no known health implication for the polymorphism under study. Subject numbers will be used to code all data forms for computer entry and storage. Study findings are reported using group data only. No information about subjects will be provided to family members, third persons or organizations. Our study personnel are trained in the protection of human subject confidentiality and are HIPAA trained and certified.

e. Financial risks to the participants.

All costs will be covered by NIAAA grant funds.

9. Benefits

a. Description of the probable benefits for the participant and for society.

This study is conducted for the advancement of science. It will provide critical safety information and examine pharmacokinetic interactions between MIFE and alcohol. It will also determine whether MIFE can be safely used for outpatient treatment of patients who may continue to use alcohol. Finally, it will provide preliminary findings of MIFE effects on alcohol craving, anxiety and intoxication.

This Phase 1 study will provide critical safety information and examine drug-drug interactions between MIFE and alcohol. Outpatient clinical trials that will meet requirements for FDA new drug approval cannot be pursued without this safety information.

10. Payment and Remuneration

a. Detail compensation for participants including possible total compensation, proposed bonus, and any proposed reductions or penalties for not completing the protocol.

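### Section 8c sets inconsistent reporting thresholds by recipient: prompt IRB and FDA reports cover a narrower set of events than the drug supplier receives

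*Combined protocol and SAP*

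**What the plan says.** Section 8c makes four statements about adverse events.

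1. One named role handles communication with the IRB and "will be responsible for reporting of AEs and SAEs". This sentence has no severity or causality condition, no time limit and no mention of the FDA.
2. "SAEs that are deemed to be severe and have a high probable or definite relationship to study procedures will be promptly reported". The named recipients are the IRB, the drug supplier and the FDA. This is the only sentence in the protocol that names the FDA as a recipient of event reports.
3. The same role "also is responsible for notifying Corcept of (a) any serious and/or unexpected adverse drug experiences", with those terms taken from 21 CFR 312.32(a). Limb (b) covers "all adverse events of special interest (AESI) that occur during the course of the Study no later than twenty-four (24) hours", the clock starting when the information is received. AESIs count at any level of severity. They include stroke, acute myocardial infarction, cardiovascular death, retinopathy and abnormal vaginal bleeding.
4. "The PI shall notify Corcept of all serious adverse events each time that a report is made to the IRB".

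Section 8b (mifepristone administration) records that the co-principal investigator holds the IND. Section 4c says: "Staff and subjects will be blind to the alcohol and MIFE doses administered during this study".

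**The concern.** Statement 2 sets three conditions that must all be met: the event is an SAE, it is severe, and it is judged to have a high probable or definite relationship to study procedures. Three features of this are troubling.

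- Seriousness and severity are different attributes. Statement 3 keeps them apart: seriousness comes from the cited regulation, and severity is a level that is ignored for AESIs. Statement 2 requires both.
- The causality bar is high. Assessors are blind to drug and alcohol dose. AUD participants also go through alcohol withdrawal, a social stress test and further alcohol, and may receive a benzodiazepine or atenolol. A confident attribution may often be hard to make, although the documents give no figure for how often.
- It is unclear whether study procedures include study drug.

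At stake is external safety oversight. Adverse events head the list of primary outcomes (section 7a), and section 9 presents the trial as a source of critical safety information on mifepristone with alcohol. Because an investigator holds the IND, nothing in the protocol lets a reader assume that notice to the supplier also reaches the FDA.

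**Working it through.** The plan gives no figure on this point and no arithmetic applies. The check sets the four statements of section 8c side by side and follows some example events through them.

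| Statement | Events covered | Severity condition | Causality condition | Recipient | Time limit |
|---|---|---|---|---|---|
| 1. General responsibility | AEs and SAEs | none | none | IRB communication mentioned; FDA not named | none |
| 2. Prompt reports | SAEs | severe | high probable or definite, to study procedures | IRB, supplier, FDA | promptly, no number given |
| 3(a). Supplier notice | serious and/or unexpected adverse drug experiences | none stated | none stated beyond the cited definition | supplier | 24 hours, if the limit governs (a) |
| 3(b). Supplier notice | all AESIs | expressly none | none stated | supplier | 24 hours |
| 4. Supplier notice | all SAEs, whenever an IRB report is made | none | none | supplier | tied to the IRB report |

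**Example events**

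- *Stroke judged only possibly related.* It is an AESI, so 3(b) sends it to the supplier within 24 hours. It fails the causality condition in statement 2, so no prompt route to the IRB or FDA is stated. This example does not depend on the text of the regulation, because 3(b) stands on the protocol's own list.
- *Serious event graded moderate.* It fails the severity condition in statement 2 even if its relationship is definite. If it is a serious adverse drug experience under the cited definition, 3(a) sends it to the supplier.
- *Unexpected drug experience that is not serious.* It goes to the supplier under 3(a). Statement 2 covers SAEs only, and expectedness does not appear in it, although the section is titled as a plan for unanticipated problems.
- *Mild abnormal vaginal bleeding.* It goes to the supplier within 24 hours under 3(b). No IRB or FDA route is stated.

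**Does statement 1 close the gap?** It assigns responsibility for the remaining events but gives no trigger, no timeline and no FDA route. It shows that reporting is not barred. It does not say when, or to whom beyond the IRB, a report goes.

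**Does study procedures include the drug?** The protocol points both ways. Table 1 lists randomization and dosing in its procedure columns. Section 8a treats procedures and drugs as separate sources of risk. The term is ambiguous.

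**Comparison with the protocol's own internal thresholds.** Participants are removed for events of moderate or greater severity (sections 4f and 7d), and the study-level rule in 7d refers to a pattern of drug-related AEs or SAEs without a severity or probability grade. The condition for prompt outside reporting is stricter than either.

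**The case against.** The strongest defence is that the supplier rule is an additional duty. It is introduced as something the same role also does, it goes to one recipient, and both rules can be followed together. A reader might infer that section 8c contradicts itself. It does not, and different thresholds for different recipients are not in themselves an error.

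Four other stronger readings are tempting, and the text does not support them.

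- *That other SAEs are never reported to the IRB or FDA.* Statement 1 assigns AE and SAE reporting generally, and statement 2 limits only what is reported promptly. The gap is an unstated route and timeline.
- *That the last sentence of section 8c brings the severity and causality conditions back into supplier notice.* It does not, because limb (a) already covers serious drug experiences independently. The sentence adds a trigger.
- *That the study-level stopping rule in 7d is disabled.* Nothing says that it depends on IRB or FDA reports. Events reach the team through the SAFTEE, administered daily on the inpatient unit and by remote contact for healthy controls, with a study physician on call. The adverse-event analysis uses the same instrument.
- *That the shortfall can be expressed as a share of severity-by-relatedness combinations.* The protocol defines no such grid and gives no event rates for one.

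The objection also rightly notes that the text of 21 CFR 312.32 and the IRB policy are not in the documents. It follows that a causality element within the term adverse drug experience cannot be excluded, and that it is unclear whether the 24-hour limit governs limb (a).

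The defence leaves the main point standing. Statement 2 is a stated rule and not merely missing detail, and followed literally it gives the IRB and FDA fewer prompt reports than the supplier.

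**Conclusion.** The point holds as an inconsistency of thresholds by recipient. Prompt IRB and FDA reporting needs a serious event that is also severe and has a high probable or definite relationship to procedures. The supplier rule has no severity condition and covers unexpected experiences and all AESIs. For events between the two thresholds, the protocol states no prompt route to the IRB or FDA.

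The size cannot be put as a number: the documents give no expected SAE count and no distribution of severity or relatedness. The analysis and sample size are untouched. The consequence is for safety oversight, and it is serious enough to correct because the affected events can include stroke and myocardial infarction.

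The conclusion rests on reading the sentences of section 8c as written and on the statement in section 8b that an investigator holds the IND. It does not rest on the content of the cited regulation. A reader might conclude that the current rule fails regulatory requirements, but the documents do not allow that judgement in either direction.

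**What to change.** Amend section 8c as follows.

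1. In the prompt-reporting sentence, delete severity as a condition added to seriousness, and delete the high probable or definite filter.
2. For the FDA, use as the trigger the seriousness and expectedness terms of 21 CFR 312.32 that the section already cites for the supplier.
3. For the IRB, state the trigger and timeline for SAEs, unexpected events and AESIs under the applicable IRB policy. These need not copy the supplier's terms, but they must be written down.
4. State that relationship is assessed to study drug and to administered alcohol as well as to procedures.
5. Say whether the 24-hour limit applies to serious and/or unexpected drug experiences as well as to AESIs.

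A short table of event type by recipient, trigger and time limit would hold all of this. The cost is protocol wording and a few more reports. No new procedure, staff, data collection or analysis is needed.
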